5.1 Time points and Visit Windows

A summary of the assessments required at each study visit is described in [\(Appendix A\)](#).

Day 1 is defined as the day of first dose of the vaccination.

Relative days after Day 1 are calculated as (assessment date – Day 1 date) + 1. Relative days prior to Day 1 are calculated as (assessment date – Day 1 date). The day prior to Day 1 is Day -1

The following visit windows will be used.

Table 5.1-1: Visit windows for previously vaccinated subjects

Statistical Analysis Plan

Sponsor Name: Seqirus
Sponsor Protocol ID: V130_10

Study part	Scheduled visit	Time interval (days)
Screening	Screening Visit	< 10 Days before Day 1
Treatment period	Clinic Visit V1	Day 1
	Reminder Phone V1	Day 3 (-1/+1 Day)
	Clinic Visit V2	Day 28 (+ 7 Days)
Follow-up Period	Safety Phone call V3	Day 90 (+ 7 Days)
	Safety Phone call V4	Day 180 (+ 14 Days)

Table 5.1-2: Visit windows for not previously vaccinated subjects

Study part	Scheduled visit	Time interval (days)
Screening	Screening Visit	< 10 Days before Day 1
Treatment period	Clinic Visit V1	Day 1
	Reminder Phone V1	Day 3 (-1/+1 Day)
	Clinic Visit V2	Day 28 (+ 7 Days)
	Reminder Phone	V2 + 2 Days (-1/+1 Day)
	Clinic Visit V3	V2 + 28 Days (+7 Days)
Follow-up Period	Safety Phone call V4	V2 + 90 Days (+7 Days)
	Safety Phone call V5	V2 + 180 Days (+14 Days)

Visit window deviations will be reviewed prior to unblinding.

5.2 Missing Values – Missing Visit.

Missing, unused and spurious data will be dealt with as such. There is no intention to implement any procedure for replacing missing data.

Titer values recorded as <1:10 (or < lower limit of quantification [LLOQ]) will be summarized as 1:5 (or ½* LLOQ).

No imputation of missing solicited or unsolicited AEs will be used but implausible measurement will be removed as described below. The percentage of subjects with missing solicited AE assessments (e.g. missing Patient Diary) and missing Safety Phone Calls or Safety Assessments will be reported for each time period.

Missing immunogenicity values are considered missing completely at random (MCAR) and therefore will not contain information that impact the result of the analysis (i.e., not informative). Imputation methods will therefore not be used.

The PPS will be used for the primary immunogenicity analysis and a supporting analysis will be performed using the FAS Immunogenicity, as noted in Section 4.4 FAS Immunogenicity.

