6.5.1.3 Statistical Methods

All statistical analyses for HAI (or MN) titers will be performed on the logarithmically transformed (base 10) values. Individual HAI titers below the detection limit (<10) will be set to half of that limit (5). Individual MN titers below the LLOQ, will be set to half of that limit ($1/2 * \text{LLOQ}$).

Co-primary immunogenicity endpoints of GMT and SCR for each virus strain contained in the vaccine will be assessed in subjects 6 Months through 47 Months of Age overall.

Statistical Analysis Plan

Sponsor Name: Seqirus
Sponsor Protocol ID: V130_10

Primary analysis will be performed in subjects 6 Months through 47 Months of Age for the Per-Protocol Set. The difference in SCRs will be presented with exact 95% CIs. Each of the four strains will be analyzed separately.

For immunogenicity data, the immunogenicity analysis will comprise a complete case analysis only, without introducing any bias. Imputation methods will not be used.

To determine the GMT ratio (adjusted analysis) a general linear model (GLM) will be fitted on log transformed (base ten) post-vaccination HAI (or MN) titer as the outcome variable and terms for covariates: vaccine treatment, pre-vaccination HAI (or MN) titer, age stratum, gender, vaccination history, age-by-vaccine interaction and study site. Potential covariate interaction effects will also be examined in the fit of the GLM. From the model, an adjusted difference in least square means (on the log scale) will be produced with 95% confidence limits. The estimated difference and the confidence limits will be back transformed to obtain an *adjusted GMT ratio* with 95% confidence limits. Each of the four strains will be analyzed separately. The adjusted GMT ratio will be the result for which the non-inferiority assessment of the HAI (or MN) GMT co-primary endpoint will be based on.

The statistical models might be reduced in case they fail to converge.

The complete set of covariates that will be used in the model to calculate the adjusted GMT ratio will include treatment group (2 treatments), pre-vaccination GMT titer (value), age strata (2 categories, 6 through 23 months or 24 through 47 months), gender (male or female), influenza vaccination received prior year (Yes or No), and investigator site (site identifier).

The GLM specification is:

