Adjusted Analysis GMT Model: Log-transformed Post-vaccination HAI (or MN) Titer = Vaccine + Age Strata + Gender + Vaccination History [y/n] + Log-transformed Pre-vaccination HAI (or MN) Titer + Site + Age Strata*Vaccine.

For any strain, the interaction term Age Strata*Vaccine will be removed from the fit of the model if it is assessed to be not significant. For all immunogenicity subgroup analysis, the interaction term will be removed in the fit of the model.

The measure of the unadjusted GMT ratio based on post-vaccination GMTs only will also be presented.

Binary data (i.e., percentages of subjects with seroconversion and with titer $\geq 1:40$) will be summarized for each group using unadjusted estimates and will be reported together with two-sided exact 95% CIs. No multiplicity adjustment to the CI levels will be implemented.

If all 8 co-primary endpoints result in a conclusion of non-inferiority, then overall non-inferiority of Seqirus QIVc compared to the US-licensed comparator QIV will be concluded.

Handling of Missing Values for Immunogenicity Data

For immunogenicity data, it may be reasonable to consider missing immunogenicity values as missing completely at random (MCAR), i.e., not informative. Therefore, the immunogenicity and key secondary analyses will comprise a complete case analysis only, without introducing any bias. Imputation methods will not be used.

Sensitivity Analyses for Handling of Missing Immunogenicity Data

To verify the robustness of the primary analysis results, an exploratory analysis may be performed, in which missing titers were imputed using *multiple imputation*. The evaluation of the robustness of the primary analysis results will be based on a pattern mixture model and a 'tipping analyses' approach using multiple imputation methods.

This sensitivity analysis, if conducted, will be based on the per-protocol analysis set and will serve to evaluate the robustness of the non-inferiority conclusions. Appendix C specifies the details of the exploratory sensitivity analysis.

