Appendix C: Sensitivity Analyses for Handling of Missing Immunogenicity Data

To verify the robustness of the primary analysis results, an exploratory analysis will be performed, in which missing titers were imputed using multiple imputation. The evaluation of the robustness of the primary analysis results will be based on a pattern mixture model and a 'tipping analyses' approach using multiple imputation methods.

This sensitivity analysis will be based on the per-protocol analysis set and will serve to evaluate the robustness of the non-inferiority conclusions.

An overview of the methods of imputation for each of the estimands GMT and binary endpoint SCR are specified below. The results based on the imputed data and the results of the same analyses performed on the original, non-imputed data using multiple imputation procedures will be compared.

GMT Missing Data Evaluation

The ANCOVA are valid when the missing data are Missing at Random (MAR). There is no reason to question MAR assumption for baseline data, but MAR cannot be established for follow-up observations.

The approach to evaluating the impact of missing serology data is based on finding the existence of evidence against the assertion that the observed results are not explained by the existence of missing data. The framework to be used for finding such evidence is the based on the Pattern Mixture Multiple Imputation (PMMI) (Little 2013). PMMI will provide assessments of missing data sensitivity.

For this exploratory analysis imputation sampling will be done using the non-missing data in pattern subsets because the expected data do not follow a defined statistical distribution. Usually PMMI implementations use Markov Chain Monte Carlo (MCMC) imputation sampling based on known statistical distributions, for example a multivariate normal. The disadvantage of sampling from non-missing data is the loss of a specified correlation structure possible when using a defined statistical distribution. The use of smaller pattern groups, however, do provide some preservation of observed within patient correlation.

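### The SAP assumes away missing titers in its main text and doubts that assumption in Appendix C; its only check is optional in one place, firm in another, and in both runs on a set that excludes almost all the children it is meant to examine

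*SAP*

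**What the plan says.** **The assumption.** SAP 5.2: "Missing immunogenicity values are considered missing completely at random (MCAR) and therefore will not contain information that impact the result". The same section adds: "There is no intention to implement any procedure for replacing missing data". SAP 6.5.1.3 is softer on the mechanism ("it may be reasonable to consider missing immunogenicity values as missing completely at random (MCAR), i.e., not informative") but not on the consequence: "the immunogenicity analysis will comprise a complete case analysis only, without introducing any bias". SAP 6.5.3.2 and Protocol 8.4.2.3.3 and 8.4.3.3.2 follow the same pattern, a hedged MCAR statement followed by an unhedged no-bias statement. Appendix C of the SAP takes another view. It does not question the "MAR assumption for baseline data, but MAR cannot be established for follow-up observations".

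**The check.** SAP 6.5.1.3: "an exploratory analysis may be performed, in which missing titers were imputed using" multiple imputation, with a second sentence that makes it conditional on being conducted. It sets no trigger and no date for the decision, and refers to Appendix C for details. Appendix C: "an exploratory analysis will be performed, in which missing titers were imputed using multiple imputation". The protocol plans no sensitivity analysis for missing titers.

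**The set.** SAP 6.5.1.3 and Appendix C both base the check on the PPS. Under SAP 4.5 the PPS is drawn from FAS Immunogenicity. Under SAP 4.4 a child enters FAS Immunogenicity only with valid serology at Day 1 and at Day 29 or 57. SAP 6.3 likewise lists the lack of either blood sample as a reason for exclusion.

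**The concern.** MCAR is a stronger condition than MAR. The SAP therefore assumes the stronger condition, and asserts its consequence, in the sections that govern the primary analysis, while its own appendix says the weaker one cannot be shown. The two kinds of co-primary endpoint also need different things. The GMT model adjusts for baseline titer, age stratum, gender, vaccination history and site, so it needs MAR given those covariates. The four seroconversion comparisons are crude, so they need missingness unrelated to response within each arm.

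The check is where that gap should be covered, and it fails on two counts. Whether it is run depends on which section is followed. And if it is run, there is almost nothing for it to work on. A CSR could then report a reassuring sensitivity analysis that had barely touched the children with missing titers.

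**Working it through.** **Step 1. Is it the only check?** The other supporting analysis uses FAS Immunogenicity, which also requires both samples. It tests the effect of protocol deviations, not of missing titers. The imputation and tipping-point analysis is the only one aimed at missing titers.

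**Step 2. What is left to impute?** Randomized and vaccinated → FAS Immunogenicity (valid serology at both visits) → PPS (no relevant deviation). A child with no Day 1 or no Day 29/57 result leaves at the first arrow. What can remain is a child with valid results for some strains and a gap for another. Appendix C describes a tipping-point graph whose axes run from zero to the number missing in each arm; on the PPS those axes have almost no length.

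**Step 3. The plan's own figures.** B strains, SCR 69% in both arms, 1450/725 evaluable, margin 10 points, one-sided 0.025 (SAP 2.3).
- SE = √[0.69 × 0.31 × (1/725 + 1/1450)] = 0.02104.
- Power = Φ(0.10/0.02104 − 1.96) = Φ(2.79) = 99.74% (stated 99.7%).
- Enrolment: 2175/0.90 = 2417 (stated 2418, which splits 1612 + 806).

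These figures are not in dispute.

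**Step 4. How informative must missingness be?** Assumptions: observed B-strain SCR of 69% in both arms; missing = 1612 − 1450 = 162 QIVc and 806 − 725 = 81 comparator, about 10% each. That 10% is the drop-out allowance; the documents give no expected rate of missing titers. Wald intervals; difference is comparator minus QIVc.

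Complete-case upper bound: 0 + 1.96 × 0.02104 = 4.1 points, a pass.

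Full-population rates, with q the SCR among missing QIVc children: QIVc = (1450 × 0.69 + 162q)/1612. Comparator = 69.0% if its missing children match completers, or (725 × 0.69 + 81)/806 = 72.1% if all of them seroconverted.

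| Missing comparator SCR | q | QIVc | Difference | Upper bound |
|---|---|---|---|---|
| 69% | 9% | 62.97% | 6.03 | 10.00 (just under) |
| 69% | 8% | 62.87% | 6.13 | 10.10 |
| 69% | 0% | 62.07% | 6.93 | 10.91 |
| 100% | 39% | 65.99% | 6.13 | 9.99 |
| 100% | 38% | 65.88% | 6.23 | 10.10 |
| 100% | 0% | 62.07% | 10.05 | 13.95 |

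The Miettinen-Nurminen interval named in SAP 6.1 gives a complete-case bound of 4.1 points and tipping values of q = 8.5% and 38.4%.

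**Step 5. The GMT ratio.** B strain, comparator/QIVc = 1/0.84, SD of log titer 1.3, unadjusted. Complete-case upper bound: exp(0.1744 + 1.96 × 0.0591) = 1.34. With 1612/806 the SE is 0.0561, which leaves 0.4055 − 0.1099 − 0.1744 = 0.1212 on the log scale. Divided by the missing fraction of 0.1005, that is 1.206. If missing comparator children match completers, the bound reaches 1.5 only when the GMT among missing QIVc children is exp(1.206) = 3.3-fold below that of QIVc completers.

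**The case against.** The strongest reply is that pairing a working assumption with a sensitivity analysis under departures from it is ordinary practice. To say that MAR cannot be established is to say that it cannot be verified, not that it is false. That stands as far as it goes. A reader might infer that the SAP admits informative missingness, or that the primary result is biased; the documents support neither. What the reply does not rescue is an unqualified claim of no bias beside an admission that the condition behind it cannot be verified.

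Nor does the design show a route to missingness that differs by arm. Children not previously vaccinated have a second dose and a third clinic visit before the endpoint sample, so they have more opportunity to drop out, but that applies to both arms under observer-blind randomization. The GMT model also adjusts for age stratum and vaccination history.

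A reader might also infer that the sponsor means to decide on the check after seeing the result. The SAP does not say so. It gives no timing at all, whereas SAP 4.5 requires the decision on duplicate FAS Immunogenicity tables to be made before unblinding. The gap permits a late decision; it is not evidence of one.

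Finally, the last row of the table might be read as a true zero difference that appears as 10 points. It is the reverse: the observed difference is zero and the 10.05 points lie in the full population. It is a worst-case bound, not a likely size.

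**Conclusion.** The concern holds as a defect of specification. The SAP is inconsistent on the missing-data assumption and on whether the check is required, and in both places the check is assigned to a set that leaves at most single-strain gaps to impute. Settling the optional/firm conflict alone would not be enough; the analysis set must change too.

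It does not follow that the noninferiority conclusion is fragile. On the assumptions in Steps 4 and 5, a flip needs strongly informative missingness: about 8–9% or fewer seroconverting among missing QIVc children against 69% in completers, about 38% or fewer if every missing comparator child seroconverted, or a 3.3-fold GMT deficit. These thresholds depend on the 10% missing fraction and on observed results at the planning values. More missing titers, or an observed difference nearer the margin, would bring them closer. That is why a working check is worth having.

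**What to change.** 1. **SAP 6.5.1.3:** replace the optional and conditional wording with a commitment that the analysis *will be performed and reported in the treatment-period CSR whatever the primary result*, in line with Appendix C.
2. **SAP 6.5.1.3 and Appendix C:** run it on all randomized, vaccinated subjects in the immunogenicity group, including those with missing pre- or post-vaccination titers, in place of the PPS. The PPS stays the primary set.
3. **SAP 5.2, 6.5.1.3 and 6.5.3.2; Protocol 8.4.2.3.3 and 8.4.3.3.2:** delete the no-bias claim and the flat MCAR statement wherever they appear. State instead that the GMT model assumes MAR given its covariates, and that the crude seroconversion comparison assumes missingness unrelated to response within arm.

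SAP 6.2 already summarizes exclusions from FAS Immunogenicity and the PPS by arm and age stratum, so most of the supporting counts are planned.

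Cost: wording changes and a modest amount of extra analysis with methods Appendix C already describes. Sample size and power are unaffected. The downside for the sponsor is that an unfavourable sensitivity result would have to be reported.

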6.5.2 Analysis of Secondary Safety Objective(s)

The analysis of safety assessments in this study will include summaries of the following categories of safety data collected for each subject:

- Vaccine exposure
- Solicited local and systemic AEs.
- Unsolicited AEs.
- SAEs, AE leading to withdrawal, NOCD

6.5.2.1 Analysis of Extent of Exposure

The number and percentage of subjects with vaccinations will be summarized overall and by vaccine group.

6.5.2.2 Analysis of Solicited Local, Systemic and Other Adverse Events Definitions

For details refer to section 7.1.1 of Study Protocol.

Analysis

Solicited Adverse Events

All solicited adverse events will be summarized according to defined severity grading scales (Table 6.5.2.2-1).

Frequencies and percentages of subjects experiencing each adverse event will be presented for each symptom severity. Summary tables showing the occurrence of any local or systemic adverse event overall and at each time point will also be presented.

Post-vaccination solicited adverse events reported for 7 days after each vaccination and will be summarized for the intervals day <30 min and day 1 to 7 by maximal

Statistical Analysis Plan

Sponsor Name: Seqirus
 Sponsor Protocol ID: V130_10

severity and by vaccine group, the latter excluding the 30-minute measurement. Injection-site erythema, ecchymosis, and induration will be summarized according to categories based on linear measurements: Type I: none (0 mm), any (1 to <10 mm, 10 to 25 mm, 26 to 50 mm, >50 mm) and Severe (>50mm).

Injection site tenderness and systemic adverse events (except fever) occurring up to 7 days after each vaccination will be summarized according to "mild, moderate" or "severe" categorization. Severity grades are defined in Tables 6.5.2.2-1 below.

Table 6.5.2.2-1 Solicited AE Grading

Symptom	Grading			
	0 (None)	Mild (Grade 1)	Moderate (Grade 2)	Severe (Grade 3)
Solicited Local AEs*				
Tenderness		For subjects less than 24 months of age at the time of the first dose of study vaccine:		
Tenderness		Minor reaction on touch	Cried/protected on touch	Cried when limb was moved/ spontaneously painful
Tenderness		For subjects 24 months of age and older at the time of the first dose of study vaccine:		
Tenderness		Does not interfere with daily activities	Interferes with daily activities	Prevents daily activity
Solicited Systemic AEs**				
Change of eating habits	None	Eating less than normal for 1 - 2 feeds / meals	Missed 1 or 2 feeds / meals	Missed more than 2 feeds / meals
Sleepiness	None	shows an increased drowsiness	sleeps through feeds / meals	sleeps most of the time and it is hard to arouse him/ her

Statistical Analysis Plan

Sponsor Name: Seqirus
Sponsor Protocol ID: V130_10

Vomiting (throwing up)	None	1 - 2 times in 24 hours	3 - 5 times in 24 hours	6 or more times in 24 hours or requires intravenous hydration
Diarrhoea (loose stools)	Fewer than 2 loose stools in 24 hours	2-3 loose stools in 24 hours	4-5 loose stools in 24 hours	6 or more loose stools in 24 hours or requires intravenous hydration
Irritability	None	Requires more cuddling and is less playful than usual	More difficult to settle	Unable to console
Shivering	None	Present but does not interfere with daily activity	Interferes with daily activity	Prevents daily activity
Temperature***	<38°C	≥38°C to <39°C	≥39°C to <40°C	≥40°C

* Injection-site erythema, ecchymosis, and induration will be summarized according to categories based on linear measurements: Type I: none (0 mm), any (1 to <10 mm, 10 to 25 mm, 26 to 50 mm, >50 mm); Type II: Grade 0 (<10 mm), any (10 to 25 mm, 26 to 50 mm, >50 mm)

** Use of antipyretics and analgesics will be summarized by frequency, by type of use (prophylactic versus treatment) and percentage of subjects reporting use.

*** Body temperature will be summarized by 0.5° C and 1.0° C increments from 36.0° C to ≥40° C and will be broken down by route of measurement and by age cohort.

Each solicited local and systemic adverse event will also be further summarized as “none” versus “any.” “Any” will include measured reactions (erythema, ecchymosis, and induration) with a diameter of at least 1 mm.

Time to onset and duration of solicited AEs will be analysed using descriptive statistics.

Implausible measurements will not be taken into consideration in the analysis.

Use of antipyretics and analgesics will be summarized by frequency, by type of use (prophylactic versus treatment) and percentage of subjects reporting use.

Body temperature will be summarized by 0.5°C and 1.0°C increments from 36.0°C to ≥40°C and will be broken down by route of measurement and by age cohort.

6.5.2.3 Analysis of Unsolicited Adverse Events

Definitions

All AEs will be characterized according to the date of occurrence related to the vaccination phase as follows:

- **Non-Treatment Emergent:** start date before the date of injection of study vaccine.
- **Treatment Emergent:** start date on or after the date of injection of study vaccine or, AE increase in severity, including to "serious" AE.

If start date is equal to the first date of injection, then "timing" variable ("Did event start before or after vaccination?") will be used to define whether the AE occur before or after the injection.

If an AE happened on the same day of injection and the time stamp is missing, then the AE is assumed to be treatment emergent.

If an AE start date is missing or unknown, the AE will be considered as emergent.

When start and/or end dates of an AE are only partially known, AEs will be categorized as emergent before, during, or after vaccination phase using the following rules:

- If the partial end date is before (<) the vaccination (i.e., year or year & month is/are before the study vaccination year or year & month) then the AE is not treatment-emergent before vaccination phase.
- If the partial start date is equal or after (≥) the first study vaccination (i.e., year or year & month is/are after or the same as the first study injection year or year & month) then the AE is considered treatment-emergent.

The **maximum event severity** is the greatest severity associated with a PT for a reported AE according to the following order: Mild < Moderate < Severe. Unknown/ Missing severity is considered as severe.

Multiple AEs with the same PT for the same subject are counted only once.

Vaccination-related AEs are those for which the cause has been evaluated by the investigator and recorded as related.

Analysis

This analysis applies to all Treatment-Emergent adverse events occurring during the study, judged either as probably related, possibly related, or not related to vaccination by the investigator, recorded in AE CRF, with a start date on or after the date of first vaccination. AE starting prior to the first vaccination will only be listed.

The original verbatim terms used by investigators to identify AEs in the CRFs will be mapped to preferred terms using the MedDRA dictionary. The AEs will then be

grouped by MedDRA preferred terms into frequency tables according to SOC. All reported AEs, as well as AEs judged by the investigator as at least possibly related to study vaccine, will be summarized according to system organ class and preferred term within system organ class. These summaries will be presented by vaccination group and by interval of study observation (Day 1 to Day 29, Day 29 to Day 181 in "previously vaccinated" subjects and Day 1 to Day 57, Day 57 to Day 209 in "not previously vaccinated" subjects). When an AE occurs more than once for a subject, the maximal severity and strongest relationship to the vaccine group will be counted.

Separate summaries will be produced for the following categories:

- SAE
- NOCDs
- Adverse events that are possibly or probably related to vaccine
- SAEs that are possibly or probably related to vaccine
- Adverse event leading to withdrawal or early termination
- Adverse event resulting in death
- Adverse events leading to a medically-attended visit during the treatment period

Data listings of all adverse events will be provided by subject. In addition, adverse events in the categories above will be provided as listed data.

